6.7.4 Vital Signs

Vital sign measurements consist of temperature, respiratory rate, blood pressure (BP), and heart rate (HR). BP and HR will be collected at screening, within 24 hours prior to dosing on Day 1, and at 2, 24, and 144 hours postdose (or at ET if applicable). Respiratory rate and temperature will be recorded at screening, within 24 hours prior to dosing on Day 1, and at 24 and 144 hours postdose (or at ET if applicable). Additional unscheduled vital signs may be recorded at other times if deemed necessary by the Investigator.

Summary statistics (n, mean, SD, minimum, median, and maximum) will be reported for vital signs results by hepatic function group (ie, Severe HI, Moderate HI, Mild HI, Normal Hepatic Function) and time point of collection. Change from baseline will be summarized in a similar manner. Baseline is defined as the last assessment, including recheck and unscheduled assessments, taken prior to dosing. Postdose unscheduled or recheck assessments will not be used in analysis. Similarly, ET results will not be included in summaries. Vital sign data will also be displayed in a data listing by hepatic function group and participant.

6.7.6 Physical Examination

Full physical examinations will be performed at screening, Day -1, and Day 7 (or ET if applicable). If the screening assessment was conducted within 4-7 days prior to dosing (Day 1), assessment will be conducted at Day -1 only if, in the opinion of the Investigator or designee, there is reason to believe they have substantially changed. Symptom-driven physical exams may be performed at other times at the discretion of the Investigator. Physical exam findings will be presented in the data listings by hepatic function group and participant.

6.7.7 Overdose

All cases of overdose will be presented in a data listing by participant.

6.7.8 Columbia Suicide Severity Rating Scale (C-SSRS)

At screening, the C-SSRS Baseline/Screening version will be administered. On Day -1 and Day 7 (or at ET, if applicable), the 'Since Last Visit' version will be administered. C-SSRS findings will be presented in the data listings by participant.

6.7.9 Extent of Exposure and Compliance

The date, time, and treatment administered will be listed by hepatic function group and participant.

6.8 Pharmacokinetic Analysis

Blood samples for assessment of plasma soticlestat (TAK-935), [REDACTED] concentrations will be collected as outlined in [Table 6.a](#) below:

Table 6.a Collection of Blood Samples for Pharmacokinetic Analysis

Analytes	Matrix	Day	Scheduled Time (Hours)*
Soticlestat, [REDACTED]	Plasma	1	Predose and 0.133, 0.25, 0.5, 0.75, 1, 1.5, 2, 4, 6, 8, 10, 14, 24, 36, 48, 72, 96, 120, and 144 hours postdose.
[REDACTED]	Plasma	1	Predose, 0.5, and 10 hours postdose.

*The actual date and time of sample collection will be recorded on the source document in the case report form.
Note: The collection time points are relative to soticlestat dosing on Day 1.

Plasma concentrations of soticlestat (total and unbound), [REDACTED] will be listed and summarized descriptively by PK sampling time according to hepatic function group (normal hepatic function and moderate and mild HI) using the following descriptive statistics: n, mean, SD, CV%, SEM, minimum, median, and maximum. Excluded concentrations will be presented and footnoted as such in the concentration table listings, and those values will be excluded from the descriptive statistics.

Individual participant concentration-time curves will be plotted by hepatic function group on linear and semi-log scales. The mean profiles of the concentration-time data will be plotted by hepatic function group on linear (with and without SD) and semi-log scales. For summary statistics and mean plots by sampling time, the nominal PK sampling time will be used. For individual participant plots by time, the actual PK sampling time will be used.

The PK parameters will be calculated from soticlestat (total and unbound), [REDACTED] concentration-time profiles using non-compartmental analysis methods where all calculations will be based on actual sampling times after dosing. The PK parameters will be summarized, defined in the CPAP, according to hepatic function group (normal hepatic function and moderate and mild HI) using the following descriptive statistics: n, mean, SD, CV%, SEM, minimum, median, maximum, geom mean (C_{max} , AUC_{∞} , and AUC_{last} only), and geom CV% (C_{max} , AUC_{∞} , and AUC_{last} only). Excluded parameters will be presented and footnoted as such in the PK parameter table listings, and those values will be excluded from descriptive statistics.

Individual plasma soticlestat (total and unbound), [REDACTED] AUC_{∞} values for participants with moderate and mild hepatic impairment as well as healthy participants will be plotted versus serum alpha-1-acid glycoprotein, serum albumin, total serum bilirubin, and INR ratio. In addition, individual plasma soticlestat (total and unbound), [REDACTED] AUC_{∞} values will be plotted versus Child-Pugh scores in participants with moderate and mild hepatic impairment.

[figure not shown]
Analysis of Variance (ANOVA)

An ANOVA will be performed on the ln-transformed C_{max} , AUC_{last} , and AUC_{∞} for total soticlestat, [REDACTED] to compare each HI group (moderate HI and mild HI) with the normal matched hepatic function group, where 90% CIs for the ratio of GMRs from each HI group versus normal matched function group will be provided. For total [REDACTED] an ANOVA will also be performed on the ln-transformed PK parameters for MRC_{max} , $MRAUC_{last}$, and $MRAUC_{\infty}$. The addition of other factors and covariates such as age, sex, and BMI on the relationship between soticlestat PK parameters and level of HI may also be investigated.

The ANOVA model will include hepatic function (Moderate HI, Mild HI, Normal Matched Hepatic Function) group as a fixed effect. GMRs and 90% CIs will be calculated from the exponentiated difference between group least squares means and corresponding 90% CIs from the analyses on the ln-transformed C_{max} , AUC_{last} , AUC_{∞} , MRC_{max} , $MRAUC_{last}$, and $MRAUC_{\infty}$. The GMRs and 90% CIs will be expressed as a percentage relative to the Normal Hepatic Function group.

The above statistical analyses will also be performed on the ln-transformed $C_{max,u}$, $AUC_{last,u}$, and $AUC_{\infty,u}$ for unbound soticlestat.

If all subjects in the healthy group are matched to both the moderate HI and mild HI groups, the ANOVA analysis will be performed using the following SAS® code. Note that due to expected differences in the variability of PK parameter values between groups, the residual variance will be estimated separately for each group with use of the repeated statement, and variance components as the covariance matrix structure:

[figure not shown]

Where 'Arm' is as described in [Section 2.0](#) where 1=Moderate HI, 2=Mild HI, 3=Normal Function. Appropriate coefficients will be used based on the input variable for arm.

If 2 healthy groups are needed to match moderate HI and mild HI separately due to differences in matching criteria, the analysis will be performed as follows:

Moderate HI versus matched Normal Function

[figure not shown]
The data will be subset to contain the moderate HI group and the matched normal function group. The ANOVA analysis will then be performed using the following SAS® code:

Appropriate coefficients will be used based on the input variable for arm.

Mild HI versus matched Normal Function

The data will be subset to contain the mild HI group and the matched normal function group. The ANOVA analysis will then be performed using the following SAS® code:

Appropriate coefficients will be used based on the input variable for arm.

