4.1.1.2 Clinical Safety and Pharmacokinetics

The PK, safety, tolerability, and/or efficacy of soticlestat have been evaluated in 6 phase 1 clinical studies in healthy participants (completed), a phase 1b/2a study in participants with DEEs (completed), and 3 phase 2 studies in participants with DS, LGS, 15q11-q13 duplication syndrome (Dup15q), cyclin-dependent kinase-like 5 (CDKL5) deficiency disorder (CDD), or complex regional pain syndrome (completed). One (1) phase 2 open-label, long-term study in participants with various DEEs, including DS, LGS, Dup15q, or CDD, 2 phase 1 drug-drug interaction studies in healthy subjects, 1 phase 1 study in participants with mild to moderate HI and healthy participants, and 3 phase 3 studies in DS and LGS patients are ongoing.

Overall, 382 participants have been enrolled in the clinical trials with soticlestat, of which 341 have received active treatment based on actual exposure and enrollment data from completed and ongoing clinical trials as of the safety data cut-off date (19 November 2021).

Soticlestat was rapidly absorbed with a median time of t_{max} of 0.25 to 0.52 hours following single-dose administration (15 to 1350 mg; Study TAK-935-101) and a median t_{max} of 0.33 to 0.5 hours following multiple-dose administration (100 to 600 mg) under fasting conditions in healthy participants (Study TAK-935-1002). When administered under fed conditions, soticlestat t_{max} was delayed by about 1.5 hours and C_{max} was decreased by 60%; however, food had little impact on the total exposure of the drug as AUC decreased by only 11% using the tablet formulation (Study TAK-935-1005). Soticlestat was shown to cross the blood brain barrier and was able to block

tracer binding to the enzyme target demonstrating a sigmoidal maximum observed effect (Study TAK-935-1003). Mean soticlestat $t_{1/2z}$ ranged from 4.39 to 7.16 hours from 200 to 1350 mg following a single-dose administration, and 3.49 to 4.83 hours across the 100 to 600 mg dose range after administration of multiple doses and similar between Days 1 and 14. [REDACTED]

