9.3.1.1 Plasma for PK Measurements

The following PK parameters will be calculated from plasma concentrations of soticlestat [REDACTED]
[REDACTED] unless otherwise specified:

AUC_{last}:

The area under the concentration-time curve, from time 0 to the last quantifiable concentration, as calculated by the linear-log trapezoidal method.

AUC_∞:

The area under the concentration-time curve, from time 0 extrapolated to infinity. AUC_∞ is calculated as AUC_{last} plus the ratio of the last measurable blood concentration to the elimination rate constant.

C_{max}:

Maximum observed concentration.

No value for [REDACTED] AUC_∞, [REDACTED] [REDACTED] will be reported for cases that do not exhibit a terminal log-linear phase in the concentration versus time profile.

No PK parameters will be calculated for participants with detectable concentrations at 2 or fewer consecutive time points.

Individual and mean plasma concentration-curves (both linear and log-linear) will be included in the final report.

Additional PK parameters may be estimated as appropriate.

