- A participant deviates substantially from the protocol defined study procedures including but not limited to dosing, dose timing, sample collection, meal timing, etc. (as determined by the Takeda Clinical Pharmacology Lead and Celerion Pharmacokinetic Scientist)
- A participant may be excluded due to vomiting

The details on PK parameter calculations and TFLs will be outlined in the clinical pharmacology and analysis plan (CPAP) and TFL Shells document including specifics on the following:

- For participants with $AUC_{\text{extrap}}\%$ greater than 20%, the descriptive and model-based statistics for AUC_{∞} will be presented with and without these participants included, if appropriate
- PK parameters presented by hepatic function group, including the units, precision, and summary statistics that will be presented in in-text and end-of-text tables
- Concentration data presented by hepatic function group, including the units, precision, and summary statistics that will be presented in end-of-text tables
- Concentration data file used for PK analysis
- PK parameter Phoenix[®] WinNonlin[®] output file used to generate the TFLs
- ANOVA model results presented in in-text and end-of-text tables
- Arithmetic mean concentration-time figures presented as in-text and end-of-text figures

- Individual concentration-time figures presented in Appendix 16.2.6.

Fraction unbound will be calculated based on the ratios of unbound concentration relative to total concentration at 0.5 and 10 hours postdose for each subject as follows:

$F_u = C_{u,0.5\text{ hrs}}/C_{0.5\text{ hrs}}$ and $F_u = C_{u,10\text{ hrs}}/C_{10\text{ hrs}}$ (where $C_u =$ unbound concentration in plasma at time t and $C_t =$ total concentration in plasma at time t).

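### Do the planned unbound soticlestat parameters lack a workable derivation because unbound drug is described at only two times?

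*SAP*

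**What the plan says.** SAP 6.8 covers total and unbound soticlestat in one sentence: "The PK parameters will be calculated from soticlestat (total and unbound), [REDACTED] concentration-time profiles using non-compartmental analysis methods". It then sets out the ANOVA for total soticlestat and adds "The above statistical analyses will also be performed on the ln-transformed" unbound Cmax, AUClast and AUC∞. Individual AUC∞ values, total and unbound, "will be plotted versus serum alpha-1-acid glycoprotein, serum albumin, total serum bilirubin, and INR ratio", and in impaired participants also against Child-Pugh score.

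SAP 6.1 describes the unbound measurements. Fu is computed per participant from "ratios of unbound concentration relative to total concentration at 0.5 and 10 hours postdose", with one formula for each time. Nothing visible says which value is carried forward, or whether they are averaged. The same section states "The details on PK parameter calculations and TFLs will be outlined in the clinical pharmacology and analysis plan (CPAP") and the TFL shells, and SAP 6.8 also refers to the CPAP for the PK parameter definitions.

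The visible protocol text (9.3.1 and 11.1.3) promises only that the unbound fraction will be determined.

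**The concern.** Read literally, the SAP asks for non-compartmental analysis of an unbound profile with two post-dose points. That cannot support an AUC∞: under Protocol 9.3.1.1 no such value "will be reported for cases that do not exhibit a terminal log-linear phase in the concentration versus time profile", and two points fit a line exactly whatever the true shape. Protocol 4.1.1.2 gives a median tmax of "0.25 to 0.52 hours following single-dose administration", so the 0.5-hour sample lies near the peak and only the 10-hour sample is clearly in the decline.

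The alternative is to multiply the total parameters by Fu. That works, but SAP 6.1 offers two Fu values per participant and no rule for choosing. The study is open-label and the moderate-impairment results have already been examined, so an unstated choice could in principle be made with the data in view.

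Protocol 4.2 and 6.4.1 name reduced protein binding as one way liver disease may alter PK. The unbound ratios bear directly on that question, and the study is meant to inform dosing recommendations.

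**Working it through.** **Sampling.** Table 6.a in SAP 6.8 lists 19 post-dose times for total soticlestat, 8 of them after 10 hours. SAP 6.1 describes unbound concentrations at 2 of the 19 and at none of those 8. A sparse row in Table 6.a has matching times, but its analyte is redacted, so nothing here rests on it.

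**Literal reading.** Protocol 9.3.1.1 bars every PK parameter, not just AUC∞, when concentrations are detectable at two or fewer consecutive times. With a predose sample below quantitation and two post-dose samples, at most two unbound values are detectable. Two-point analysis would therefore yield no unbound Cmax, AUClast or AUC∞ for anyone. The protocol rules this reading out, so it cannot produce a misleading result.

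**Scaled reading.** For each participant, unbound parameter = Fu × total parameter. On the log scale, ln AUCu = ln AUC + ln Fu, so

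unbound ratio = total ratio × (geometric mean Fu, impaired ÷ geometric mean Fu, normal).

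Replacing the 0.5-hour Fu by the 10-hour Fu multiplies the unbound ratio by

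k = (Fu10/Fu0.5 in impaired) ÷ (Fu10/Fu0.5 in normal).

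The choice cancels from the ratio whenever k = 1. Fu need not be constant over time; it need only change by the same proportion in both groups. Individual unbound values and their plots would still shift.

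**Size if k is not 1.** The total ratios are the interim moderate-impairment figures in Protocol 4.2. The range of k is an assumption, and the 0.5-hour Fu is taken as equal in the two groups. Each entry is total ratio × k, in percent.

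| Parameter | Total ratio | k = 0.80 | k = 0.90 | k = 1.00 | k = 1.10 | k = 1.25 |
|---|---|---|---|---|---|---|
| Cmax | 214.93 | 171.9 | 193.4 | 214.9 | 236.4 | 268.7 |
| AUClast | 316.47 | 253.2 | 284.8 | 316.5 | 348.1 | 395.6 |
| AUC∞ | 299.38 | 239.5 | 269.4 | 299.4 | 329.3 | 374.2 |

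No corresponding total ratio is available for mild impairment.

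**Is there reason to expect k to differ from 1?** The two Fu values are taken at different total concentrations. Protocol 4.1.1.2 reports a mean half-life that "ranged from 4.39 to 7.16 hours from 200 to 1350 mg following a single-dose administration", and a second study reports single-dose values of 5.075 to 8.695 hours. If decline from 0.5 to 10 hours is no slower than the terminal phase, the fall over 9.5 hours is at least 2^(9.5/half-life): 2^(9.5/4.39) = 4.48 and 2^(9.5/8.695) = 2.13. This is only a rough guide. The half-lives span several doses, and in the second study tmax was 0.5 to 0.75 hours, so the 0.5-hour sample may precede the peak. Nothing visible reports concentration-dependent binding. A concentration difference would matter only if it altered binding by different proportions in the two groups.

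**The case for a change.** The best case for acting is that the SAP is where the inferential analysis is fixed. Its non-compartmental sentence does not fit its own two-time description, and one added line would settle the Fu rule at no cost in samples or participants. A further gap supports this. SAP 6.1 sets values below quantitation to zero, so an unquantifiable unbound sample at 10 hours could give Fu = 0, which cannot be log-transformed.

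The inconsistency in wording stands, and so does the absence of a visible Fu rule. The risk built on them does not. The SAP twice points to the CPAP for PK calculations and definitions. Without that document it cannot be said that the choice is open, only that it is not repeated in the SAP. SAP 6.8 lists total and unbound concentrations by sampling time, so both Fu values can be recovered for each participant and any ratio recomputed with the other one. A zero Fu would have to be set aside before taking logs, in line with SAP 6.1 leaving zeros out of geometric means.

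**Conclusion.** This is a gap in visible detail that analysts would fill sensibly, and no change to the plan follows. The protocol's own rule excludes two-point analysis, and the per-participant Fu formulas point to scaling the total parameters. The remaining question, which Fu to use, belongs to the document to which the SAP delegates it.

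The size is zero if Fu changes by the same proportion over time in both groups. Under the assumed relative change of 0.80 to 1.25, the choice moves the moderate-impairment unbound AUC∞ ratio from 299.4% to between 239.5% and 374.2%. The documents contain no Fu values with which to narrow that range.

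The total-soticlestat comparison and Fu itself are unaffected. The SAP states no hypotheses or decision rules, and the sample size is justified as descriptive, so no formal decision rests on the unbound ratios.

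Two limits apply. The CPAP was not available, so it is not known that it names the Fu. Redactions also mean that an unbound analyte in the densely sampled row, or an exploratory endpoint involving unbound drug, cannot be excluded. The first would make the literal reading feasible; the second would raise the standing of the unbound ratios without altering the total-drug analysis.

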6.9 Patient Reported Outcomes (PROs) and Health Care Utilization Endpoints Analysis

Not applicable

6.10 Preliminary Analysis

After all participants in moderate HI arm and the matching 12 participants in the matched normal hepatic function arm have completed the treatment period, an informal preliminary PK data analysis is planned and may additionally leverage historical control PK data in healthy participants to gain an initial estimate of the effect of moderate HI on the PK of soticlestat [REDACTED].

This amendment was written following the preliminary analysis. The preliminary analysis indicated higher impact of moderate HI on soticlestat PK than predicted based on model-based simulations. The Sponsor decided to remove the participants with severe HI from the study because soticlestat will not be recommended to use in subjects with severe HI. The amendment is created to evaluate the impact of mild HI on the PK of soticlestat.

6.11 Interim Analysis

No interim analysis is planned for this study.

6.12 Data Monitoring Committee/Internal Review Committee/ [Other Data Review Committees]

Not applicable

7.0 REFERENCES

Not applicable

8.0 CHANGES TO PROTOCOL PLANNED ANALYSES

Description as in protocol	Change	Rationale for Change
Incidence of clinically significant abnormal values for laboratory evaluations,	The analysis will not be performed.	This endpoint is included as part of standard AE reporting and will not be analyzed separately.

Description as in protocol	Change	Rationale for Change
vital signs, ECG parameters, and C-SSRS		
Vital signs assessments will be summarized by group and point of time of collection and a shift table describing out of normal range shifts will be provided.	A shift table will not be generated for vital signs	The normal criteria are not defined, and analysis of out of normal range shifts is not required.
C-SSRS results will be summarized by group and point of time of collection and a shift table describing out of normal range shifts will be provided	C-SSRS data will not be summarized	Normal criteria are not defined, and summary is not required. Data will be listed and discussed in the CSR.

9.0 APPENDIX

9.1 Changes From the Previous Version of the SAP

Changes made from the previous version of the SAP that have a **material impact to the planned statistical analysis methods** are described below. In addition, there were textual changes purely to improve the flow, organization and clarity. As these represent cosmetic changes with no impact to the planned statistical analyses, they are not included in the table below.

SAP Section	Impacted Text (shown in bold)	Change	Rationale for Change
All	All instances of severe	Changed to mild	Per protocol amendment, the severe hepatic impairment cohort was changed to a mild hepatic impairment cohort. All references to the severe cohort in this SAP have been changed to mild.

9.2 Data Handling Conventions

Not applicable

